2.1.1 General definitions

Study treatment: KAF156, Lumefantrine solid dispersion formulation (LUM-SDF) are part of investigation treatments. Coartem® is used as standard of care (SOC). They are referred to as study treatments in the document.

Treatment group name will be used in statistical analyses and outputs. Abbreviated treatment group description that concatenates drug code, dosage, no. of doses, and food intake in the form of “KAFxxxmg/LUMyyyymg- QD x X food intake” will be used as the column headers in the CSR outputs. If all the treatment groups are not accommodated within a page of a post text table, the names may be shortened such as by deleting the unit “mg”.

For example, the initial treatment groups in Run-in Cohort will be displayed as:

- KAF400mg/LUM240mg- QDx2-Fed
- KAF400mg/LUM240mg-QDx2-Fasted

As per study design, other dose combinations of KAF/LUM with different food recommendation may also be used. It is also possible to use treatment for 3 days. Treatment groups for each of the combinations will be used accordingly.

Baseline: The last measurement made prior to administration of the first dose of study treatment. Note this may include measurements taken on the day of randomization (e.g. lab, ECG, vitals).

If a patient did not receive any dose of study treatment then the randomization date will be used as the date of first dose of study treatment.

Study day: Study day will be calculated with respect to the first dose of study treatment. The first day of administration of study treatment (first dose) is defined as Day 1. Day -1 will be the day before Day 1. Day 0 does not exist. Due to the multiple assessments collected more than once for a day in the treatment phase for some variables, the study day calculation is based on the treatment start date and time.

For the assessments that are performed more than once for a day:

$\text{Study day} = \text{Integer}(\text{datetime of assessment} - \text{datetime of first dose of study treatment}) / (60 * 60 * 24) + 1.$

For assessments that are performed once for a day: study day = date of assessment – date of first dose of study treatment + 1.

For assessments collected prior to Day 1, study day = date of assessment - date of first dose of study treatment.

Tail of KM plots: Since patients may come to visit earlier or later than the targeted day and the tail of KM plots after the day of last planned assessment is not reliable due to small numbers of patients at risk, the time to event/censoring will be reset to Day 43 if it's greater than 43. This principle will be used for relevant tables using the KM method.

Body temperature: Body temperature is measured using different routes (oral/rectal/tympanic/axillary), which will lead to variations in the readings. Therefore, all the temperature readings will be standardized with respect to axillary equivalent as follows for the reporting purpose:

Body temperature (Axillary temperature) = Other routes (oral/tympanic/rectal equivalent) - 0.5°C

For body temperature, date and time of measurement should be collected as per the protocol. However, the current CRF captures only the date but not time due to which actual body temperature collection time will be missing in the clinical database for Run-in and its repeats cohorts. This technical glitch in the database will be corrected before the initiation of Cohort 1. For the statistical analysis of body temperature data, planned time will be considered as actual time of collection where the actual time is missing.

Non-rescue medication: Non-study concomitant antimalarial drugs without experiencing treatment failure.

2.1.1.1 Definition of treatment failures

Early Treatment Failures (ETF)

Patient will be classified as ETF upon meeting any of the following criterion

- Development of danger signs or severe malaria on Day 2, Day 3, Day 4 in the presence of parasitaemia.
- Parasitaemia on Day 3 higher than Day 1 count irrespective of axillary temperature.
- Parasitaemia on Day 4 with axillary temperature $\geq 37.5^{\circ}\text{C}$.
- Parasitaemia on Day 4 equals to or more than 25% of count on Day 1.

Late Clinical Failure (LCF)

Patient will be classified as LCF upon meeting any of the following criterion

- Development of danger signs or severe malaria on any day from Day 5 to Day 43 in the presence of parasitaemia without previously meeting any of the criteria of early treatment failure.
- Presence of parasitaemia and axillary temperature $\geq 37.5^{\circ}\text{C}$ on any day from Day 5 to Day 43 without previously meeting any of the criteria of Early Treatment Failure.
- Missing body temperature assessment in presence of parasitemia will be classified as LCF.

Late Parasitological Failure (LPF)

- Presence of parasitaemia on any day from Day 8 to Day 43 and axillary temperature $< 37.5^{\circ}\text{C}$ without previously meeting any of the criteria of Early Treatment Failure or Late Clinical Failure.

Note: If the temperature is measured using other routes, such as oral/tympanic/rectal, the corresponding threshold for fever is 38.0°C . Danger signs or severe malaria is recorded as adverse events. The adverse event start date of danger signs or severe malaria will be used in the determination of ETF and LCF. Only *P. Falciparum* asexual form is used for parasitaemia/parasite in the assessments of treatment failure and ACPR in [Section 2.1.1.2](#) below. The body temperature assessment closest to the blood smear assessment date will be used.

2.1.1.2 Definition of ACPRs

Uncorrected ACPR at Day X where X=15, 29, or 43

- A patient is considered as non-responder at Day X if the patient experiences an ETF, LCF from Day 5 to Day X, or LPF from Day 8 to Day X.
- A patient is also considered as non-responder if the parasite is not cleared by Day X unless the patient discontinues the study prior to Day X without ETF or LCF or LPF, in which case the response is considered as missing. Note that if a patient takes non-study antimalaria medications during the treatment period, the patient is considered as non-responder.

- A patient is considered as responder (Uncorrected ACPR) at Day X if the patient is not classified as a non-responder at Day X and the patient has a malaria blood film showing absence of parasite at Day X or later if Day X is missing.
- The response for a patient is considered as missing/undetermined if the patient is not classified as a non-responder prior to Day X and the malaria blood film result at Day X is missing and not followed by a subsequent negative result.

PCR-corrected ACPR at Day X where X=15, 29, or 43

- A patient is considered as non-responder at Day X if the patient experiences an ETF or LCF from Day 5 to Day 7.
- A patient is also considered as non-responder if the initial parasite is not cleared by Day X unless the patient discontinues the study prior to Day X without ETF or LCF or LPF, in which case the response is considered as missing. Note that if a patient takes non-study antimalaria medications during the treatment period, the patient is considered as non-responder.
- A patient is considered as non-responder at Day X if the patient has a parasite recrudescence from Day 8 to Day X
- A patient is considered as responder (corrected ACPR) at Day X if the patient is not classified as a non-responder by Day 7 and has negative results at Day X based on microscopy and PCR genotyping.
- A patient is considered as responder at Day X if the patient is not classified as a non-responder at Day X and the patient has a malaria blood film showing absence of parasite at Day X or later if Day X is missing.
- A patient is considered as responder at Day X if the patient is not classified as a non-responder at Day X and the patient has a malaria blood film showing new infection **at** Day X using PCR genotyping or later if Day X is missing.
- The response for a patient is considered as missing/undetermined (e.g., due to missing PCR data or miss blood smear data) if
 - The patient, not classified as non-responder at Day X, has parasite present from Day 8 to Day X for which the PCR genotyping of recrudescence or new infection is not determined.
 - The patient is not classified as a non-responder at Day X and the malaria blood film result at Day X is missing and not followed by a subsequent negative result/new infection.
 - The patient has parasite cleared by Day 7 but has a new infection/negative PCR prior to Day X, ie, new infection/negative PCR at a visit causes PCR-corrected ACPR status unknown in later visit(s).

Note - In the context of derivation of ACPR status at Day X, the 'Day X' is referred to as the Day X analysis visit. For e.g., ACPR status at Day 29 is referred to as the ACPR status at Day

29 analysis visit. Analysis visit X will be derived using the day actual visit as defined in Tables 5-5 and 5-6. Unscheduled visits will be considered for deriving analysis visit. Assessments 'prior to Day X' will be identified using study day of assessments prior to Day X. The outcome of PCR-corrected ACPR and uncorrected ACPR at a given day is categorized as responder or non-responder to distinguish from failure used in early treatment failure, late clinical failure or late parasitological failure. With this notation, ACPR rate is the proportion of responders.

Recurrence of parasitaemia after 7 days is considered as non-responder for uncorrected ACPR. We reclassify such patient as responder for PCR-corrected ACPR at the visit if recurrence of parasitaemia after 7 days is due to new infection and a patient did not take rescue medication. A new infection at a visit causes PCR-corrected ACPR status unknown at later visit(s). Whether the recurrence of parasitaemia after 7 days is due to recrudescence or new infection is determined and provided by the central laboratory. Negative PCR will be handled similarly to new infection and categorize the patient as PCR corrected responder.

The above definitions of ACPRs are purely based on the malaria blood film and PCR results without consideration for taking concomitant anti-malaria drugs. In statistical analyses, some responses may be overridden for patients who take concomitant anti-malaria drugs (see [Sections 2.5 and 2.7](#)).

Fever Clearance is defined (in patients with temperature of $\geq 37.5^{\circ}\text{C}$ -axillary equivalent at baseline) as the time of the first measurement of at least 2 consecutive temperatures of $< 37.5^{\circ}\text{C}$ measured at least 24 hours apart.

Time to parasite clearance (PCT) is defined as time from the first dose until the first total and continued disappearance of asexual parasite forms which remained at least a further 48 hours

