### **12.4.1 Definition of primary endpoint(s)**

The primary efficacy variable is the PCR corrected Adequate Clinical and Parasitological Response (ACPR) at Day 29 (Cohorts 1 and 2 pooled).

In case that Cohort 2 stops early, such as after the first 24 patients, the study objectives will be assessed based on Cohort 1 data alone.

A patient is considered as PCR-corrected ACPR at Day 29 if the patient does not meet any of the criteria of ETF (up to Day 4), LCF (Day 5 to Day 29) or LPF (Day 8 to Day 29), and is absence of parasitaemia on Day 29 irrespective of axillary temperature unless the presence of parasitaemia after 7 days (Day 8 or later) is due to reinfection based on PCR genotyping.

A presence of parasitaemia after 7 days of treatment initiation is considered as a reinfection only if the parasitaemia is clear before Day 8 and none of the parasite strain(s) detected on Day 8 or later match with the parasite strain at baseline based on PCR genotyping.

Treatment failures after 7 days due to reinfection based on PCR genotyping are not considered as failure for PCR-corrected analyses but will be considered as failure for PCR uncorrected analyses.

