2.2 Analysis sets

Randomized set

All patients who are randomized into the study.

Full analysis set (FAS)

FAS will be comprised of all patients from Randomized set who take at least one dose of study treatment during the treatment period and whose baseline *P. Falciparum* asexual parasitaemia count is greater than 0. Following the intent-to-treat principle, patients will be analyzed according to the treatment group assigned to at randomization.

Unless otherwise specified, misrandomized patients will be excluded from the FAS.

Misrandomized patients, if identified from IRT, include patients who are screen-failures, but have been randomized by the investigator before eligibility was finally assessed or mistakenly, and have not been treated. If patients were re-screened and successfully randomized, they will be included in the randomized set according to the treatment assigned in the last randomization.

Safety set (SAF)

Safety set includes all patients who take at least one dose of study drug during the treatment period. Patients will be analyzed according to treatment received. In particular, patient will be analyzed in the same treatment group as randomized if s/he receives at least one dose of the study medication of that group. For the PK run-in cohort, all patients to receive the same dose in either fasted or fed condition.

Per-protocol set (PPS)

Per-protocol set will be comprised of patients in FAS who

- did not have any important protocol deviations affecting efficacy
- took at least 80% dosages of randomized study medication(s). If a patient vomited the original dose but did not vomit the replacement dose, the patient is considered as taking the dose of study medication. Since a partial compliance, such as 83%, etc., can be calculated based on the actual dosage taken (see [Section 2.4.1](#)), this allows patients to take partial dosages.
- did not take non-study medications with anti-malaria activity prior to Day 29 visit unless experiencing any treatment failure (ETF, LCF, LPF) (e.g new infections between Day 8 and Day 29), and PCR corrected ACPR status at Day 29 is defined, ie, at least one of the following criteria is met:
 - a. classified as treatment failure before Day 8 (see [Section 2.1.1](#))
 - b. had parasitaemia present on Day 8 or later without parasite clearance before (eg., parasite present Day 15 and parasite was not cleared before Day 15).
 - c. absent from parasitaemia at Day 29 or later,

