2.5.4.1 Analysis of PCR-corrected ACPR rate using Kaplan-Meier method

For the FAS, the proportion of patients with PCR-corrected ACPR at Day 29 and 95% CI will be also estimated using the Kaplan-Meier method ([Stepniewska and White 2006](#) and [WHO 2015](#))

Event = PCR-corrected non-responder during the study (same as at Day 15, Day 43, see [Section 2.1](#)). The event time is the first time when the patient becomes a non-responder based on PCR-correction. If a patient parasite is not cleared at all, Day 7 is considered as the event time.

The PCR-corrected responder rate at Day 29 is estimated by the survivor function at Day 29 using the Kaplan-Meier method.

Rule for censoring:

The following censoring rules will be applied to the patients who were not non-responder

- Patients who had a new infection with *P. falciparum* or other species without *P. falciparum* recrudescence on or after Day 8 will be censored at the first time of the PCR that indicate the infection or blood smear with other species.
- Patients who received non-rescue antimalarial medication for other infections [REDACTED] will be censored at the first time of antimalarial medication.
- Patients who have parasites at Day 8 or later but cannot be determined as recrudescence or new infection due to missing PCR genotyping will be censored at the time of the first malaria blood film with presence of parasites on or after Day 8.
- Other patients not classified as non-responder will be censored at the time of last parasitemia assessment.

An asymptotic two-sided 95% CI for the difference in proportion of responders between two treatment groups will be calculated from the z-test statistic distribution based on the variance of individual proportion using the Greenwood formula.

The confidence interval will be constructed as: $(r_k - r_c) \pm Z_{\alpha/2} * SE_d$;

where,

r_k = Kaplan-Meier estimate for the treatment group at time t,

r_c = Kaplan-Meier estimate for the control group at time t,

$SE_d = \sqrt{(SE_k^2 + SE_c^2)}$,

SE_k = estimated standard error for the treatment group based on Greenwood's formula,

SE_c = estimated standard error for the control group based on Greenwood's formula,

$Z_{\alpha/2}$ = z-statistic = probit(1- α /2) from a normal distribution function, $\alpha = 0.05$.

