2.7.2.5 Time to event analysis for Recrudescence

Recrudescence is defined as appearance of asexual parasites after clearance of initial infection with a genotype identical to that of parasites present at baseline. Recrudescence must be confirmed by PCR analysis.

Incidence rates of recrudescence at Days 15, 29 and 43 will be estimated by the Kaplan-Meier method based on the subset of FAS patients who have clearance of initial infection by Day 7.

Time to event (recrudescence) will be calculated from the time of first study medication to the date of first event if a patient experiences the event and is censored at the first use of non-study antimalarial medication for purpose other than recrudescence or at the time of last parasite assessment otherwise. Undetermined treatment failures due to missing PCR data will be considered as censored at the time of treatment failure. The between treatment difference will be evaluated exploratorily using a log-rank test separately by cohort and stratified by cohort for Cohorts 1 and 2 pooled if cohort 2 does not stop early; otherwise for Cohorts 1 and 2 separately.

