5.7.4 Summary of treatment outcome assignment

The below table provides treatment outcome assignments for both uncorrected and PCR-corrected ACPR at a given Day, say D where D can be 15, 29, or 43, for various specific scenarios.

Table 5-13 Derivation Criteria of uncorrected ACPR and PCR- corrected ACPR

Criteria	PP Analysis Set (PPS)		ITT Analysis Set	
	Treatment Outcome uncorrected ACPR	Treatment Outcome PCR-adjusted ACPR	Treatment Outcome uncorrected ACPR	Treatment Outcome PCR-adjusted ACPR
1. Completed up to Day (D) without re-emergence (new infection/ recrudescence) of parasites after initial clearance	Responder	Responder	Responder	Responder
2. Missing assessment on Day (D), but parasite free (No P. falciparum asexual parasites) after Day (D).	Responder	Responder	Responder	Responder
3. Missing assessment on Day (D), new infection (confirmed by PCR result) at first assessment after Day (D).	Non-responder	Responder	Non-responder	Responder
4. Early treatment failure from Day 2 to Day 4.	Non-responder	Non-responder	Non-responder	Non-responder
5. Late clinical failure from Day 5 to Day 7.	Non-responder	Non-responder	Non-responder	Non-responder
6. Receive non-study anti-malarial medication during the treatment period	Excluded from PPS	Excluded from PPS	Non-responder	Non-responder
7. Recrudescence before or on Day (D) (thus on or after Day 8 to [D])	Non-responder	Non-responder	Non-responder	Non-responder
8. New infection/PCR negative on Day (D).	Non-responder	Responder	Non-responder	Responder
9. New infection/PCR negative before Day (D) (thus on or after Day 8 to before (D))	If D <=29, excluded from PPS; If D=43, Non-responder	If D <= 29, excluded from PPS; if D=43, non-responder/	Non-responder	Non-responder/responder/KM-censoring

		responder/KM-censoring;		
10. Re-emergence before or on Day (D) but PCR result is indeterminate or missing.	Non-responder	Excluded from PPS if D ≤ 29 or non-responder/KM-censoring if D=43	Non-responder	Non-responder/KM-censoring
11. Missing assessment on Day (D), recrudescence (confirmed by PCR result) at first assessment after Day (D).	If D=29, excluded from PPS; if D=15, non-responder/KM-responder; NA for D=43	If D=29, excluded from PPS; if D=15, non-responder/ KM-responder; NA for D=43	Non-responder/ KM-responder	Non-responder/ KM-responder
12. Other Plasmodium species on Day (D) (in the absence of P. falciparum).	Responder	Responder	Responder	Responder

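### PCR-corrected ACPR: the SAP has no rule that reliably fails a child whose initial parasites are still present at Day 8 but gone by Day 29, whereas the protocol makes that child a failure

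*SAP*

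**What the plan says.** **Protocol 12.4.1.** ETF, LCF up to Day 29 and LPF from Day 8 to Day 29 all rule out PCR-corrected ACPR, except for late parasitaemia due to reinfection. Late parasites are "considered as a reinfection only if the parasitaemia is clear before Day 8" and no strain matches baseline.

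**SAP 2.1.1.2, PCR-corrected ACPR at Day X (15, 29 or 43).** A child is a non-responder:
- "if the patient experiences an ETF or LCF from Day 5 to Day 7";
- for persistence: "A patient is also considered as non-responder if the initial parasite is not cleared by Day X" (with an exception for study discontinuation);
- for a recrudescence between Day 8 and Day X.

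The first responder bullet asks that the child has not failed by Day 7 and is negative at Day X on both film and PCR. A further bullet asks only that the child is not already a non-responder and has a negative film at Day X. LPF is listed in the uncorrected definition just above but not in the corrected one.

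**Elsewhere in the SAP.**
- Section 2.7.2.5 defines recrudescence as "appearance of asexual parasites after clearance of initial infection" with the baseline genotype.
- Section 2.2 counts Day 29 status as defined, for the per-protocol set (PPS), if a child "had parasitaemia present on Day 8 or later without parasite clearance before". It does not say what the status is.
- Table 5-13, row 1, gives responder for "Completed up to Day (D) without re-emergence (new infection/ recrudescence) of parasites after initial clearance". No row describes persistence.
- Section 2.5.4.1 (Kaplan-Meier) says: "If a patient parasite is not cleared at all, Day 7 is considered as the event time".
- Section 4 lists no change to the protocol's analyses.

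**The concern.** The two documents use different clocks for the same event. The protocol sets a fixed cut-off: parasites seen from Day 8 that were not cleared before Day 8 cannot be reinfection, so they are a failure. The SAP uses a cut-off that moves with the analysis day, so an infection that persists at Day 8 and clears by Day 29 escapes the only bullet written for persistence.

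This rule defines the primary endpoint in the set used for the non-inferiority test. Without a clear rule, the same record can be scored in more than one way at programming, and one of those ways turns a protocol failure into a success.

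**Working it through.** **1. One record, both documents.** The child has no ETF, no LCF by Day 7, is afebrile with a positive film on Day 8 and never negative before, and has a negative film on Day 29.

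| Rule | Met? | Result |
|---|---|---|
| Protocol 12.4.1: LPF from Day 8, not clear before Day 8 | Yes | Failure |
| SAP 2.1.1.2: ETF, or LCF Day 5 to 7 | No | – |
| SAP 2.1.1.2: initial parasites not cleared by Day 29 | No, film negative by then | – |
| SAP 2.1.1.2: other antimalarials in the treatment period | No; dosing lasts 2 or 3 days (protocol 6.1.4), so rescue at Day 8 falls outside | – |
| SAP 2.1.1.2: recrudescence, as defined in 2.7.2.5 | No, nothing cleared first | – |
| SAP 2.1.1.2: not a non-responder, film negative at Day 29 | Yes | Responder |
| SAP 2.1.1.2, if the central laboratory reports recrudescence | Possible | Non-responder |
| SAP 2.1.1.2 closing note: late recurrence is reclassified only if new infection and no rescue | Possible, if rescued | Non-responder |
| SAP 2.1.1.2: parasites from Day 8 without a PCR classification | Possible | Undetermined |

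The protocol gives one answer and the SAP gives three.

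**2. Is the child in the tested set?** Yes. The PPS criterion in SAP 2.2 treats uncleared parasitaemia as evaluable. Table 5-14 excludes later antimalarial use only when there was no treatment failure, and this child has LPF. It excludes new infection and unclassifiable parasitaemia only when parasites had cleared first. Even the undetermined version of this child therefore stays in the PPS, although SAP 2.5.3 expects no missing outcome there.

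**3. The plan's own figures** (protocol 12.8.1, SAP 3.1.1: 92 per group, 95% in both, margin 10%, one-sided 2.5%).
- Standard error = √(2 × 0.95 × 0.05 / 92) = 0.0321.
- Power = Φ(0.10/0.0321 − 1.96) = 87.5%, against a stated figure of at least 87%. Reproduced.
- 92/0.84 = 109.5, so 110 per group and 220 in total. Reproduced.

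The point changes neither figure.

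**4. Weight of one child.** 1/92 = 1.09 points. At 95% response, about 0.05 × 92 = 4.6 failures per arm are expected. Take 87/92 Coartem responders and an unstratified Wald interval, as an approximation to the planned Mantel-Haenszel interval:
- 84/92 on KAF156/LUM-SDF: lower limit −10.65%, not shown;
- 85/92: lower limit −9.30%, shown.

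With the Newcombe (Wilson uncorrected) interval, planned if Cohort 2 stops early, the switch comes one child later: −10.08% at 85/92 and −8.72% at 86/92.

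**5. Illustration only.** Assume true protocol-defined rates of 85% and 95%, exactly at the margin, and let a share q of the KAF156/LUM-SDF arm alone be scored responder instead of failure. The chance of declaring non-inferiority is the sum of Bin(a; 92, 0.85 + q) × Bin(b; 92, 0.95) over all (a, b) with a lower limit above −10%.

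| q (assumed) | Wald | Newcombe |
|---|---|---|
| 0% | 3.4% | 2.4% |
| 1% | 5.4% | 3.9% |
| 2% | 8.6% | 6.3% |
| 3% | 13.1% | 9.8% |
| 5% | 27.7% | 21.5% |

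**The case against.** The strongest reply is that a sensible programmer would probably fail this child.
- Afebrile parasitaemia on Day 8 is LPF, so under protocol 8.3.2 the sample is genotyped, and SAP 2.1.1.2 leaves the classification to the central laboratory. A baseline match may be reported as recrudescence. The after-clearance wording sits in a secondary time-to-event section, not in the ACPR definition.
- The closing note of SAP 2.1.1.2 speaks against reclassifying a rescued child.
- The PPS criterion lists persistence beside failure before Day 8 and recrudescence, which suggests that failure was intended.
- Table 5-13 takes the worst case when several criteria apply, and its row 1 concerns re-emergence, not persistence.
- ETF and LCF to Day 7 already catch febrile or severe persistence, and high Day 4 counts.

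Most of this stands as evidence of intent, but none of it is a rule that settles the case. A call of recrudescence conflicts with the SAP's only definition of the term. The closing note is worded for recurrence, and it treats a negative PCR like new infection without repeating the protocol's clearance condition. The PPS criterion gives evaluability, not an outcome. The worst-case rule needs a matching non-responder row, and there is none. The rescue rule in SAP 2.5.4 covers only patients outside the PPS and makes them non-responders only for recrudescence.

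On Kaplan-Meier, a reader might infer that only parasites that never clear count as an event. That is not so: SAP 2.5.4.1 defines the event as any PCR-corrected non-response during the study, and the sentence on never clearing only sets an event time. A child still uncleared at Day 15 is an event. The gap there is limited to clearance between Day 8 and the Day 15 visit.

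**Conclusion.** The SAP is wrong as written on this point. It replaces the protocol's fixed Day 8 cut-off with a moving one and omits LPF. As a result, responder, non-responder and undetermined can each be supported for a record that the protocol scores as failure. The change is not declared, and it touches the primary endpoint in the tested set.

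Two stronger readings are not supported. A reader might infer that every such child becomes a Day 29 responder; the laboratory classification, the note on rescue and the undetermined rule all leave other outcomes open. A reader might also infer that type I error is inflated to the levels in the last table. Those figures assume a share of affected children that no document gives, place all of them in one arm, and assume that each is scored responder. Equal misclassification in both arms would largely cancel. What can be said is that each affected child is worth about 1.1 points, and that near the margin one child can change the conclusion.

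**What to change.** - **SAP 2.1.1.2:** state that parasites present on any film from Day 8 to Day X, without clearance before Day 8, make the child a PCR-corrected non-responder at Day X, whatever the later clearance, rescue or PCR classification. A child uncleared on Day 8 is then a non-responder at Days 15, 29 and 43, as protocol 12.4.1 requires. Tying the rule to parasites seen from Day 8 avoids failing a child whose first negative film is the Day 8 film and who stays negative, whom the protocol does not fail on this ground.
- **Table 5-13:** add this case as a non-responder row in the PPS and ITT columns.
- **SAP 2.5.4.1 and 2.7.2.2:** state that such a child is an event at Day 7/8 even if parasites clear later.
- If the departure from the protocol is intended, declare and justify it in SAP Section 4 instead.

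The cost is SAP wording and one derivation line, with no new data and no change to sample size or power. The reported ACPR may be slightly less favourable.
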